#### **8.4.1 Laboratory evaluations**

Clinically significant abnormalities must be recorded as either medical history/current medical conditions or adverse events as appropriate.

In all cases, the investigator must document in the source documents the clinical considerations (i.e., result was/was not clinically significant and/or medically relevant) in allowing or disallowing the patient to continue in the study.

A central laboratory will be used for analysis of all safety specimens collected. Details on the collection, shipment of samples and reporting of results by the central laboratory are provided to investigators in the central laboratory manual.

All abnormal lab results must be evaluated for criteria defining an AE and reported as such if the criteria are met. For those lab AEs, repeated evaluations are mandatory until normalization of the result(s) or until the result is no longer considered to be clinically significant.

Test category	Test name
Hematology	Hematocrit, Hemoglobin, Platelets, Red blood cells, White blood cells, Differential (Basophils, Eosinophils, Lymphocytes, Monocytes, Neutrophils, Other)
Chemistry	Albumin, Alkaline phosphatase, alanine aminotransferase (ALT), aspartate aminotransferase (AST), Gamma-glutamyl-transferase (GGT), Lactate dehydrogenase (LDH), Bicarbonate, Calcium, Magnesium, Phosphorus, Chloride, Sodium, Potassium, Creatinine, Creatine kinase, Direct Bilirubin, Total Bilirubin, Total Protein, Blood Urea Nitrogen (BUN) or Urea, Uric Acid, Amylase, Lipase, Glucose (non-fasting), C-reactive protein (CRP), D-Dimer, Ferritin
Coagulation	Prothrombin time (PT), International normalized ratio (INR), Activated partial thromboplastin time (APTT)
Pregnancy Test	Serum / Urine pregnancy test

#### **8.4.2 Electrocardiogram**

Not evaluated.

#### **8.4.3 Pregnancy and assessments of fertility**

A condom is required for all sexually active male patients to prevent them from fathering a child AND to prevent delivery of study treatment via seminal fluid to their partner. In addition, male patients should not donate sperm for the time period specified above.

All pre-menopausal women who are not surgically sterile will have pregnancy testing at screening and end of study (EOS). Additional pregnancy testing might be performed if requested by local requirements.

**Screening:** Women who have been on stable highly effective contraception in the last 3 months prior to enrollment will have a urine beta-human chorionic gonadotropin ( $\beta$ -HCG) pregnancy test with minimum sensitivity 25 mIU/mL. In other cases, e.g., no previous contraception or unstable (e.g., due to missed days of oral contraceptive or change in contraceptive method), women will have a serum  $\beta$ -HCG pregnancy test.

**EOS:** Urine  $\beta$ -HCG pregnancy test. In the case of a positive test at the EOS, the pregnancy will be reported. The site will contact the participant at least monthly and document the participant's status until the pregnancy has been terminated or until 6 months after the delivery. The outcome of the pregnancy will be reported to the sponsor without delay within 24 hours if the outcome is a serious adverse experience (e.g., death, abortion, congenital anomaly, or other disabling or life-threatening complication to the mother or newborn).

The result of each pregnancy test will be reported on an eCRF.

### **Assessments of fertility**

Medical documentation of oophorectomy, hysterectomy, or tubal ligation must be retained as source documents. Subsequent hormone level assessment to confirm the woman is not of child-bearing potential must also be available as source documentation in the following cases:

1. Surgical bilateral oophorectomy without a hysterectomy
2. Reported 12 months of natural (spontaneous) amenorrhea with an appropriate clinical profile.

In the absence of the above medical documentation, follicle stimulating hormone (FSH) testing is required of any female patient regardless of reported reproductive/menopausal status at screening/baseline, otherwise the contraception measures described for women of child-bearing potential apply.

#### **8.4.4 Appropriateness of safety measurements**

[figure not shown]
The safety assessments selected are standard for this indication/patient population.

### **8.5 Additional assessments**

#### **8.5.1 Pharmacokinetics**

Venous blood samples will be collected for assessment of free ensovibep (ensovibep not bound to target) and total ensovibep (sum of ensovibep not bound to target and ensovibep bound to target) concentrations in serum at the visits defined in the assessment schedule.

Pharmacokinetic samples will be obtained and evaluated in all participants and at all dose levels except the placebo group. Free and total ensovibep will be determined by validated analytical methods. Concentrations will be expressed in mass per volume units.

Results will be presented in the Bioanalytical Data Report.

The PK parameters will be determined using the actual recorded (elapsed) sampling times relative to start of infusion and non-compartmental method(s) with Phoenix WinNonlin (Version 6.4 or higher).

The following PK parameters will be determined: Cmax, Tmax, AUClast, AUCinf, T1/2,  $\lambda_z$ , Vz, CL. Additional pharmacokinetic parameters may be calculated as necessary. Further details are provided in the SAP.

The linear trapezoidal rule will be used for AUC calculation. Regression analysis of the terminal serum elimination phase for the determination of T1/2 will include at least 3 data points after Cmax. If the adjusted R2 value of the regression analysis of the terminal phase will be less than 0.75, no values will be reported for T1/2, AUC, CL, and Vz.

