Study design	
This is a randomized, double-blind, placebo-controlled, multicenter study of ensovibep (MP0420) in ambulatory adult patients with symptomatic COVID-19. The study has two parts: a Phase 2 dose-ranging study to select the best dose over the therapeutic range (Part A) to progress into Phase 3, and a confirmatory Phase 3 safety and efficacy study of the dose determined in Part A (Part B).
 
Screening will be used to determine eligibility. Randomization and treatment will be conducted on Day 1 (screening can optionally be done up to 3 days earlier, or also at Day 1). Study duration for individual patients is <math>91 \pm 7</math> days for both Parts.
 
Part A
 
This dose-ranging part of the study will include at least 400 randomized patients in four arms (3 active arms and one placebo arm), randomized 1:1:1:1 to receive ensovibep (75 mg, 225 mg, or 600 mg) or placebo, administered as a single intravenous (i.v.) infusion over 60 minutes, and stratified by risk for COVID-19 disease progression ("high-risk patients" versus "not at high-risk patients").
 
Part B
 
Recruitment will begin in Part B once the most safe and efficacious dose has been selected from Part A based on the primary [day 8 viral load] analysis. Part B will recruit 1717 patients randomized 1:1 to either the selected dose of ensovibep or placebo, administered as a single i.v. infusion over 60 minutes. An interim analysis for early efficacy will be conducted when at least 50% of patients have completed the Day 29 assessments. Patients will be stratified by risk for COVID-19 disease progression ("high-risk patients" versus "not at high-risk patients").

Study population	
The study will recruit ambulatory symptomatic adult patients diagnosed with COVID-19 with onset of symptoms within 7 days prior to dosing and with a positive rapid antigen test on the day of dosing.

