#### **Initial human safety, tolerability, and PK results from MP0420-CP101**

The safety-focused no-observed-adverse-effect-level (NOAEL) approach was used to determine FIH doses of 3, 9 and 20 mg/kg for MP0420-CP101 (summary of the relevant pre-clinical safety data can be found in the Investigator's Brochure [IB]). Dosing of healthy volunteers with single i.v. infusions of 3 and 9 mg/kg (8 mg/kg would equate to a single dose of 600 mg in a 75 kg person) was completed. MP0420-CP101 Phase 1 investigation of the safety, tolerability, and PK of MP0420 in healthy participants is ongoing, and to date MP0420 was assessed as safe and well-tolerated and no serious adverse effects have been reported. A 20 mg/kg cohort will be enrolled in Q1 2021. Based on this, the proposed doses of 75, 225, and 600 mg are expected to be safe in SARS-CoV-2 infected patients.

Preliminary PK data from cohort 1 (i.v., 3 mg/kg) and cohort 2 (i.v., 9 mg/kg) are available. The estimated half-life for MP0420 across cohorts is approximately 14.4 days (mean, range: 11.4-24.0 days). Slightly greater than dose-proportional increases in exposure were observed from cohort 1 to cohort 2 (3.8-fold increase in AUC with a 3-fold increase in dose). Cohort 1 exhibited serum concentrations on Day 14 of  $31.9 \pm 6.3$  ug/mL (mean  $\pm$  standard deviation [SD]), which corresponds to  $378 \pm 75$  nM (mean  $\pm$  SD), and is  $> 1000$ -fold above the IC50 determined for MP0420 in infected Vero E6 cells. Cohort 1 exposures approximate the 225 mg single dose, which is the mid-dose in this dose-range finding study.

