2. Urine test with minimum sensitivity 25 mIU/mL for WOCBP in stable contraception for at least 3 months before screening and at EOS. Serum test in other cases, e.g., no previous contraception or unstable (e.g., due to missed days of oral contraceptive or change in contraceptive method).
3. Birth control method will be documented only in source data.
4. Two PK samples: 15 minutes and 90 minutes after end of administration (defined as end of the saline flush).
5. FDA's recommended 14-item symptom assessment ([FDA 2020a](#)) to be used (from which the 8-point score can also be extracted). Options: Daily documentation by patient until Day 15 via PRO-tool, then weekly; or dedicated phone assessment on pre-specified days.
6. Although it is anticipated that most patients will be screened and administered study medication on the same day (Day 1) at Visit 1, patients may have screening procedures performed up to 3 days before study medication administration (Days -3 to -1) and study medication administered on Day 1. The following screening procedures do NOT need to be repeated pre-dose in such case: Informed consent, demographics, complete medical history, height, and weight.
7. Patients who discontinue before Day 29 will complete all V7 (Day 29) assessments as their EOS visit except for the Long-COVID-19 or SF-36 questionnaires.
8. Patients discontinuing between Day 29 and Day 91 to complete V9 (Day 91) assessments as EOS visit.

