2.9 Pharmacokinetic endpoints

For all analyses in this section, the PK analysis set will be used.

The PK analysis is specified as a secondary objective in Part A

Free (ensovibep not bound to target) and total (sum of ensovibep not bound and ensovibep bound to target) concentration in serum will be summarized by treatment in each Part at Day 1 pre-dose, Day 1 post-dose (at minute 15 and minute 90), Day 3, Day 8, Day 15, Day 29, Day 61 and Day 91, including the frequency (n, %) of concentrations below the LLOQ and reported as zero. Median concentrations and median log(concentration) over scheduled time-points will be presented graphically by treatment group.

The following PK parameters will be determined: C_{max} , T_{max} , AUC_{last} , AUC_{inf} , $T_{1/2}$, λ_z , V_z , CL . PK parameters will be summarized by treatment in each Part and will include mean (arithmetic and geometric), SD, and CV (arithmetic and geometric), median, minimum, and maximum. The maximum concentration or peak after a dose administration (C_{max}) and the area under the concentration versus time curve (AUC) will be provided.

In addition, population PK modeling will be performed and data from other clinical studies may be pooled. If performed, results of the population PK modeling may be reported separately and will not be part of the CSR.

[REDACTED]

[REDACTED]

[REDACTED]

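### Linear trapezoidal AUC across 14- to 32-day late sampling gaps biases AUC upward and clearance downward by about 3% to 7% on average in patients followed to Day 91 (minor)

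*Protocol*

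**What the plan says.** Protocol 8.5.1 plans a non-compartmental analysis: "The following PK parameters will be determined: Cmax, Tmax, AUClast, AUCinf, T1/2", together with the terminal rate constant, Vz and CL. It fixes the integration method without qualification: "The linear trapezoidal rule will be used for AUC calculation". It leaves further detail to the SAP. SAP 2.9 lists the same parameters and their summaries but gives no integration rule, so the protocol's rule stands.

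For the early samples, Table 8-1 has "Two PK samples: 15 minutes and 90 minutes after end of administration", and the dose is "administered as a single intravenous (i.v.) infusion over 60 minutes". The later visits in SAP 2.9 are "Day 3, Day 8, Day 15, Day 29, Day 61 and Day 91". Table 8-1 allows ±3 days at Day 15, ±5 at Day 29, ±5 at Day 61 and ±7 at Day 91.

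On elimination, Protocol 4.2 reports from healthy volunteers: "The estimated half-life for MP0420 across cohorts is approximately 14.4 days (mean, range: 11.4-24.0 days".

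Two limits on what is reported also come from Protocol 8.5.1. "Pharmacokinetic samples will be obtained and evaluated in all participants and at all dose levels except the placebo group". And "If the adjusted R2 value of the regression analysis of the terminal phase will be less than 0.75, no values will be reported" for half-life, AUC, CL and Vz.

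**The concern.** The Day 29 to 61 and Day 61 to 91 gaps are 32 and 30 days, which is 32/14.4 = 2.2 and 30/14.4 = 2.1 mean half-lives. Over such a gap the concentration curve is clearly convex, and a straight line between its ends lies above it. The integration error therefore has a known sign and does not shrink with more patients. AUCinf inherits it. CL is dose divided by AUCinf, so it is biased downward, and Vz (CL divided by the terminal rate constant) falls in the same proportion.

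Characterising PK is a secondary objective of Part A, with the calculated parameters as its endpoint. SAP 2.9 also plans population PK modelling, but allows its results to be reported separately and outside the clinical study report. The non-compartmental AUC and CL may then be the only such values in that report.

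**Working it through.** The documents give no AUC or CL figure for this trial, so there is nothing to reproduce. The check is a direct calculation.

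**Inputs from the documents:** 60-minute infusion; samples 15 and 90 minutes after the end of administration, then Days 3, 8, 15, 29, 61 and 91 (elapsed time = study day − 1); half-life 14.4 days (11.4 to 24.0).

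**Assumptions:** one-compartment decline (two-compartment as sensitivity); flush time taken as zero; terminal slope from the last three points; concentrations quantifiable to the last visit.

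**Step 1, error within one gap.** For exponential decline over a gap of D days, linear trapezoid / true area = (x/2)·coth(x/2), with x = ln2 × D / T½. At 14.4 days:
- D = 14: x = 0.674, ratio 1.038
- D = 32: x = 1.540, ratio 1.190
- D = 30: x = 1.444, ratio 1.168

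**Step 2, weight by each gap's share of the total area.** The share is 2^(−start/T½) − 2^(−end/T½), in elapsed days. At 14.4 days:
- Day 15 to 29: 0.510 − 0.260 = 25.0%; × 3.76% = 0.94 points
- Day 29 to 61: 0.260 − 0.056 = 20.4%; × 19.0% = 3.9 points
- Day 61 to 91: 0.056 − 0.013 = 4.3%; × 16.8% = 0.7 points
- Day 3 to 8 and Day 8 to 15 together: about 0.3 points

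The sum is about 5.8%, which is the AUCinf bias, because the extrapolated tail is correct under this model. CL bias = 1/1.058 − 1 = −5.5%.

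**Step 3, the stated half-life range.**

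| T½ (d) | 14-d gap | 32-d gap | 30-d gap | AUClast | AUCinf | CL | AUCinf, linear-up/log-down |
|---|---|---|---|---|---|---|---|
| 11.4 | +6.0% | +29.7% | +26.3% | +7.2% | +7.2% | −6.7% | −0.03% |
| 14.4 | +3.8% | +19.0% | +16.8% | +5.9% | +5.8% | −5.5% | −0.03% |
| 24.0 | +1.4% | +7.0% | +6.2% | +3.1% | +2.9% | −2.8% | −0.02% |

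**Step 4, sensitivity.**
- *Visit windows, 14.4 days.* Visits at Days 24, 66 and 98 (42-day middle gap): AUCinf +10.4%, CL −9.4%. Visits at Days 18, 34, 56 and 84: AUCinf +3.8%, CL −3.6%.
- *Assumed distribution phase* (40% to 60% of the initial concentration, half-life 1 to 2 days): AUCinf +6.9% to +8.2% at 14.4 days, and +3.7% to +10.0% over the stated range. Linear-up/log-down leaves +0.7% to +2.3%.
- *Shorter follow-up, 14.4 days.* To Day 29: AUCinf +1.2%, AUClast +1.6%. To Day 15: AUCinf +0.3%. At 11.4 days, follow-up to Day 29 gives 23.2% × 0.77% + 22.7% × 1.51% + 24.5% × 5.97% = about 2.0% on AUCinf.
- *Residual error* (assumed CV 5% to 30%, log-scale half-life SD 0.2, 40,000 simulated patients per CV): mean AUCinf bias stays at +5.8% to +5.9%. The linear result exceeded the linear-log result in every simulated patient. AUCinf exceeded the patient's own true value in 99% of patients at CV 5%, 89% at 10%, 72% at 20% and 64% at 30%.

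**The case against.** The other side has several good points.

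- **The late-gap percentages overstate the matter.** An error of 19% or 30% belongs to one interval holding 16% to 20% of the area at those half-lives. The whole-profile error is 3% to 7%, against a between-subject spread of about 20% (Day 14 concentration 31.9 ± 6.3 µg/mL in Protocol 4.2; 6.3/31.9 = 20%). This stands.
- **No decision depends on it.** PK is summarised descriptively. Part B dose selection rests on the viral-load MCP-Mod result, clinical events, symptoms and safety (Protocol 12.4.2, SAP 2.5.2). SAP 2.14 expects PK data beyond Day 8 to be incomplete at the Part A primary analysis. If half-life is similar across doses, the bias largely cancels between arms. This stands too.
- **The rule is pre-specified and applied alike to all arms.** True, but that does not make it unbiased for the absolute AUC and CL values.

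Two stronger readings are tempting. A reader might infer that AUC is overstated in every patient. The integration error is upward wherever the decline is convex, but the reported value need not be: assay noise can outweigh it, early leavers carry little bias, and placebo patients and poor terminal fits have no AUC reported.

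A reader might also infer that the rule hides faster elimination in patients with antidrug antibodies. The readable text plans no AUC or CL comparison by antibody status, and the effect would be small. With an assumed half-life of 7 days against 14.4, a true CL ratio of 14.4/7 = 2.06 would read as about 2.00. With 5 days, 2.88 would read as about 2.8. Half-lives of 5 to 7 days do not come from the documents.

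**Conclusion.** The point holds as a minor one. For patients followed to Day 91, the stated rule biases non-compartmental AUClast and AUCinf upward by about 3% to 7% on average over the stated half-life range, and by about 6% at the mean. It biases CL downward by about 3% to 7%. The AUC bias can reach about 10% with the widest windows at the mean half-life, or with an assumed distribution phase at the shortest. It is about 1% on AUCinf when follow-up ends at Day 29 at the mean half-life, and less when it ends earlier.

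The direction follows from the convexity of the decline. The size rests on near-exponential decline, the healthy-volunteer half-lives carrying over to patients, and concentrations staying quantifiable to Day 91. The documents give no assay limit against which to check the last of these. The calculation uses the Part A schedule; SAP 2.9 lists the same sampling days for each Part. The viral-load primary endpoint, MCP-Mod and the population PK model are unaffected.

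**What to change.** In Protocol 8.5.1, at the next amendment, replace the integration sentence with: *AUC will be calculated with the linear-up/log-down trapezoidal rule (linear while concentrations rise, are equal or are zero; logarithmic while they fall).* State the same in SAP 2.9. If only the SAP is changed, record it as a departure from the protocol in SAP Section 4, which now declares none.

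No extra samples or visits are needed, and data already collected can be analysed this way through a setting in the non-compartmental software. The cost is a wording change that goes through the approval steps in Protocol 14.1, so it need not trigger an amendment on its own. Reported AUC values will be a few percent lower than under the linear rule, which should be noted if they are set beside AUCs from other studies calculated linearly.

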## 8.5.2 Biomarkers

### 8.5.2.1 Rapid antigen test

An immunoassay (COVID-19 Rapid Antigen Test) for the qualitative detection of SARS-CoV-2 antigens in nasopharyngeal swab samples will be used to confirm ongoing presence of viral load with SARS-CoV-2 prior to randomization.

### 8.5.2.2 SARS-CoV-2 viral load

SARS-CoV-2 viral load will be quantified during the course of the study according to the Assessment Schedule (Table 8-1 and Table 8-2). Viral load will be measured to determine its correlation with other clinical and pharmacodynamic parameters by the use of a validated RT-PCR test on a sample of specimen of the respiratory mucosa (nasopharyngeal swab), reported as copies of viral RNA per milliliter of transport media (copies/mL). The same sample will be used to analyse viral genome to determine and monitor the virus genetic variants. Instructions for sample collection, processing, and shipment will be provided in the Laboratory Manual.

[REDACTED]

[REDACTED]

[REDACTED]

[REDACTED]

[REDACTED]

#### **8.5.2.5 Soluble biomarkers**

Serum for analysis of cytokines and other markers of inflammation shown to be implicated in the severity of COVID-19 (e.g., interleukin [IL]-6, IL-8, etc.) will be collected at the indicated timepoints throughout the study as shown in [Table 8-1](#) and [Table 8-2](#). Changes in circulating concentrations of serum biomarkers associated with inflammation and disease progression will be assessed in the ensovibep treatment groups as compared to the placebo groups. The association between changes in disease related biomarkers with clinical endpoints will be evaluated. Samples may also be evaluated on a broad proteomics discovery platform (e.g., SomaScan). Sample collection and processing will be described at the Lab Manual.

#### **8.5.3 Immunogenicity**

Immunogenicity testing will be performed on each patient according to the Assessment Schedule ([Table 8-1](#) and [Table 8-2](#)). All immunogenicity samples will be listed by treatment group, patient and visit/time and the instructions for sample collection, numbering, processing, and shipment will be provided in the Laboratory Manual.

The presence of antibodies against ensovibep will be determined using a stepwise approach. Samples will be assessed using a validated screening immunoassay. Positive results from the screening assay will be re-assessed in a validated confirmatory assay. Confirmed samples will then be analyzed using a titration assay.

## **9 Study discontinuation and completion**

### **9.1 Discontinuation and completion**

#### **9.1.1 Interruption of study drug infusion and study discontinuation**

Study treatment consists of a single dose infusion. In case of interruption of infusion due to AEs, time and relative amount of study drug administered should be recorded in the CRF, as well as restart and end time (as applicable). Adverse event should be captured in appropriate CRF. Treatment of AEs should follow standard of care (symptomatic treatment).

Infusion of study drug must be interrupted or stopped under the following circumstances:

- Patient/guardian decision.
- Suspected hypersensitivity reaction occurs, including any of the following: fever, chills, dyspnea, headache, myalgia, hypotension. Immediate interruption of the infusion to administer study treatment is required in such cases. In case of fever, restart of infusion is permitted under close medical surveillance if the fever subsides with antipyretic treatment. In case of chills, dyspnea, headache or myalgia, restart of infusion is permitted under close medical surveillance if the event was already a noted symptom of COVID-19 at study enrollment and it subsides without treatment within 15 minutes.
- Emergence of any other infusion related reaction: anaphylaxis, angioedema, urticaria, rash, administration site reaction. Immediate interruption of the infusion to administer study treatment is required in such cases. Restart of infusion is not recommended.

Patients who discontinue study treatment or who decide they do not wish to participate in the study further should NOT be considered withdrawn from the study UNLESS they withdraw their consent (see [Section 9.1.2](#) ‘Withdrawal of Informed Consent’ section). **Where possible, they should return for the assessments indicated** in the Assessment Schedule. If they fail to return for these assessments for unknown reasons, every effort (e.g., telephone, e-mail, letter) should be made to contact the patient/pre-designated contact as specified in the lost to follow-up section. This contact should preferably be done according to the study visit schedule.

